6.4.3.2 Secondary Objectives Analyses

Adjusted Analyses and Planned Subgroup Analyses

We will perform other analyses as needed aimed at obtaining adjusted assessments of treatment effectiveness, adjusting for baseline patient characteristics (covariates). The objectives of these analyses are to estimate the influence of covariates on the outcome and to use covariates to improve the estimated difference between treatment groups. The Poisson regression model (link=log) with robust standard errors stratified by study site will be used to identify and estimate the effect of multiple prognostic factors on the probability of spontaneous vaginal delivery and other categorical outcomes, with results summarized as adjusted risk ratios. For continuous secondary outcomes such as maximal newborn weight loss and PIMS and MBFES survey scores, quantile regression, e.g., modeling 50th percentile, will be considered to adjust for prognostic factors. Interaction tests will be used to determine whether the effectiveness of nipple stimulation therapy significantly differs across these subgroups. These analyses will be considered exploratory in nature and will not be viewed as providing confirmatory tests of hypotheses.

The following pre-specified subgroup analyses will be conducted:

1. Study site
2. Amniotic membrane status (intact versus ruptured) at enrollment
3. Presence versus absence of maternal diabetes (inclusive of pre-gestational and gestational diabetes)
4. Insurance type (commercial versus public insurance)
5. Maternal race (Black versus White versus Other)
6. Obesity (obese versus non-obese)

In separate models, each of these sub-group variables will be included as an additional covariate in the models for outcomes of interest, plus their interaction with treatment variable; followed by stratified analyses (by each of the above variables) of the effect of treatment on each outcome of interest.

Data Analysis Plan for the Biospecimen Sub-Study:

The primary comparison for Aim 1 is the difference in biomarker concentration or MS counts from baseline to 2 hours of treatment between patients performing nipple stimulation therapy and those receiving IV oxytocin. Secondary comparisons evaluate the change with labor induction versus spontaneous labor. This unadjusted between-group comparison of the within-group change will be based on a Student's t-test, with a supportive analysis using Analysis of Covariance (ANCOVA) where the baseline biomarker level will be a covariate in a mean response profile model (MRP), which allows for different variances and covariances across time. The primary exposure variable will be treatment group with either compound symmetry (CS) covariance or heterogenous compound symmetry covariance (HCS) to account for the within-patient correlation in biomarker values across the time points of data collection; and the choice between the two covariance matrices will be made using a likelihood ratio test (LRT)

as these are nested models. Results will be summarized as estimated means of fold change at adequate contractions for each group and the between-group mean differences, with surrounding 95% Confidence Intervals. By specifying the model as an MRP, we can also conduct any comparisons of means (within/between groups across time), by using linear contrasts and the multivariate Wald Test. In the adjusted analyses, we will include in the MRP as covariates the between-group differences identified in the between-group comparisons. In a sensitivity analysis, since we will know the timing of each measurement relative to the initiation of treatment, we will use the actual time (compare linear, polynomial or spline effect of time) instead of the categorical time point in a linear mixed effects model (LME) with a random intercept for each woman and a possible random slope for each woman (also tested using an LRT). All biomarkers listed in the Table will be analyzed in the same manner, as all will be treated as continuous variables. For the exploratory hypothesis using the time to active labor, we will use a joint modeling approach: time to active labor modeled jointly with the mean trajectory of change over time in biomarker values; this model will allow us to estimate the between-group differences in the time to active labor, as it is also influenced by the biomarker values within each group.

Data Analysis Plan for the Milk Biospecimen Sub-Study:

The primary comparison will be looking at milk composition before and after birth for participants in the nipple stimulation group. We will use Student's t-test to compare the paired milk samples from the same individuals.

Secondary comparison will be looking into milk composition between patients performing nipple stimulation therapy and those receiving IV oxytocin versus spontaneous labor at 12, 24, 48 and 72 hours postpartum. We will account for multiple measurements for each participant (if multiple samples will be collected) and those will be used for a mixed effect model. Structural equation model will be used for modeling the effect of additional variables (delivery mode, intentions to breastfeed, feeding frequency, maternal intention to feed etc.) on milk biomarkers and breastfeeding outcomes.

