2) The sample size of 988 for the primary outcome will be sufficient to detect a 9.4% or 10.8% absolute difference in breastfeeding as the sole source of nutrition (BSSN) at the time of delivery hospitalization postpartum discharge with 80% power and 90% power, respectively (two-sided test, $\alpha=0.05$). This represents the difference between an expected BSSN rate of 47% in the setting of synthetic oxytocin infusion without nipple stimulation (average rate at the study sites based on institutional data) and 56.4% (with 80% power) or 57.8% (with 90% power) with nipple stimulation therapy.

3) Assuming a 15% attrition rate at 2 weeks postpartum (the time frame for our primary cost-effectiveness analysis in Aim 3), the sample size of 988 will have 90% power for detecting a standardized effect size of 0.22 for the between-group difference in cost and difference in quality adjusted life years (QALY) (two-sided test, $\alpha=0.05$). This is considered a small effect size based on conventional criteria, hence if we observe an even larger effect size, we should be sufficiently powered.

The sample size for this biospecimen trial is based on the primary comparison, specifically the difference in primary biomarkers from baseline to after 2 hours of treatment between patients performing nipple stimulation therapy and those receiving IV oxytocin. Sample size calculations are based on differences between non-laboring and laboring patients from prior reports (Table). Sample size was determined to achieve 80% power to detect a difference with a two-tailed alpha level of 0.05. The final sample size of 48 per exposure group is based on the largest sample size required (IL1beta). Therefore, there is more than adequate power for the remainder of the biomarkers of interest.

To detect a 10 mM difference in sodium concentration between the intrapartum nipple stimulation therapy group and the immediate synthetic oxytocin infusion group at 48 hours postpartum, with a standard deviation of 20 mM, 80% power, and a significance level of 0.05, a sample size of 32 participants per group is required. Accounting for an expected 30% dropout rate, we plan to recruit 46 participants per group.

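### The biospecimen sub-study ranks a t-test on change above the baseline-adjusted ANCOVA that it already plans; ANCOVA is at least as precise, by an amount the protocol does not let one fix

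*Protocol*

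**What the plan says.** Protocol section 6.4.3.2, in the data analysis plan for the biospecimen sub-study, defines the main contrast: "The primary comparison for Aim 1 is the difference in biomarker concentration or MS counts from baseline to 2 hours of treatment", nipple stimulation against IV oxytocin. The test chosen for that contrast is the two-sample t-test, with no baseline term; the sentence that fixes it opens "This unadjusted between-group comparison of the within-group change will be based on a". Baseline adjustment takes second place, described there as coming "with a supportive analysis using Analysis of Covariance (ANCOVA) where the baseline biomarker level will be a covariate". The model meant is a mean response profile. No reason is given for this order.

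For the further adjusted analyses the same section says "we will include in the MRP as covariates the between-group differences identified in the between-group comparisons".

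Section 6.4.2 gives the power basis: "Sample size was determined to achieve 80% power to detect a difference with a two-tailed alpha level of 0.05". It sets 48 per exposure group from the IL1beta row of its table. The differences come from earlier reports on non-laboring and laboring patients, and the table does not say whether its SDs are SDs of change or of single measurements. Neither section gives a correlation between the baseline and 2-hour values. Section 5.3.1 gives 192 trial participants for this sub-study, plus 48 women in spontaneous labor.

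**The concern.** The two arms are randomised 1:1 and baseline is measured. Subtracting baseline assumes that a woman who starts one unit higher also ends one unit higher. Where the true within-arm slope is below 1, as it is whenever the SDs are equal and rho is below 1, subtraction over-corrects. It adds noise and carries part of any chance baseline imbalance into the estimated effect. With 48 per group that imbalance has a standard error of sqrt(2/48) = 0.20 baseline SDs, so it is not negligible in one realised sample. ANCOVA estimates the slope and avoids both problems. The sub-study would therefore draw its main inference from the less precise of two analyses that it will run in any case.

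The covariate rule for the adjusted analyses is a smaller, separate weakness. Under randomisation, differences found between the arms are chance, so the rule selects on observed imbalance rather than on prognosis and leaves the adjusted model unfixed until the data are seen.

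**Working it through.** **Inputs.** Two-sided alpha 0.05, 80% power and 48 per group (section 6.4.2). Oxytocin difference 24.25% with SD 40.8; IL1b 1.56 with SD 2.19; PAI-1 2.27 with SD 2.655; ICOS ligand 3.07 with SD 2.73 (table in 6.4.2). Assumed, because the protocol does not give them: rho, and k = 2-hour SD divided by baseline SD.

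**The plan's own figures.** n per group = 2(1.96 + 0.84)²(SD/difference)².
- Oxytocin: 2 × 7.85 × (40.8/24.25)² = 44.4, so 45, as stated.
- IL1b: 2 × 7.85 × (2.19/1.56)² = 30.9, so 31 (32 with the t distribution), against 48 stated. An n of 48 would need an SD of about 2.70.

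The row said to fix 48 therefore does not follow from its printed inputs. That is a separate matter, but it means the nominal 80% is not the power of every marker.

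**Variance comparison.** Take the baseline variance as 1 and the same covariance within each arm.
- Change score: 1 + k² − 2·rho·k.
- ANCOVA: k²(1 − rho²).
- Change score minus ANCOVA: (1 − rho·k)², which is never negative. It is zero only when rho·k = 1, that is, when the true slope is 1.
- With k = 1 the ratio of ANCOVA to change-score variance is (1 + rho)/2.

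**Power at 48 per group.** The standardised difference that gives the t-test 80% (df 94) is 0.578. ANCOVA power uses 0.578/sqrt(variance ratio) in the noncentral t with df 93.

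| rho (k = 1) | Variance ratio | ANCOVA power | Gain, points |
|---|---|---|---|
| 0.3 | 0.65 | 93.5% | 13.5 |
| 0.5 | 0.75 | 89.9% | 9.9 |
| 0.7 | 0.85 | 86.0% | 6.0 |
| 0.8 | 0.90 | 84.0% | 4.0 |
| 0.9 | 0.95 | 82.0% | 2.0 |

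Simulation (10,000 runs per rho) gave 93.0%, 89.5%, 85.1% and 81.8% for ANCOVA at rho 0.3, 0.5, 0.7 and 0.9.

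**Unequal SDs, rho 0.5.** The variance ratio is k²(0.75)/(1 + k² − k).
- k = 0.8: ratio 0.571, power 96.0%.
- k = 1.25: ratio 0.893, power 84.2%.
- k = 1.5: ratio 0.964, power 81.4%.
- k = 2: ratio 1.000, power 80.0%, no gain.

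**By marker, printed inputs, table SDs read as SDs of change, k = 1, rho 0.5.**
- Oxytocin: 82.2% to 91.4%, about 9 points.
- IL1b: 93.2% to 97.9%, about 5 points.
- PAI-1: 98.6% to 99.8%, about 1 point.
- ICOS ligand: no visible change.

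**If the table SDs are cross-sectional instead (k = 1).** Change uses 0.578/sqrt(2(1 − rho)) and ANCOVA 0.578/sqrt(1 − rho²). The t-test and ANCOVA have 65.8% and 83.6% at rho 0.3, 80.0% and 89.9% at rho 0.5, and 95.1% and 97.5% at rho 0.7.

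**If 192 means 96 per arm.** At the same standardised difference the t-test already has 97.8%, so the gain cannot exceed about 2 points.

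**The case against.** The case for leaving the plan alone has substance. The change-score t-test is unbiased over randomisation and controls type I error. It does use baseline, by subtraction, so it would be wrong to say that the primary analysis ignores it. The ANCOVA is planned and will be reported. The gain depends on two quantities that the protocol does not give. The model in 6.4.3.2 itself allows variances to differ over time, and section 2.1 describes a dose-dependent oxytocin rise under infusion, so a larger 2-hour SD is plausible. All of this stands, and it limits the size of the point.

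The scale also matters. Oxytocin is tabled as a percent change and results are to be summarised as fold change. ANCOVA on the 2-hour value, raw or log, does not estimate a mean percent change. The two analyses target the same effect only on a common additive scale, so the scale must be settled with the model.

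A reader might infer three stronger things that the documents do not support. One is a flat loss of about 10 power points: that needs rho near 0.5, equal SDs and a starting power near 80%. Another is that running both analyses leaves open which p-value counts: calling the ANCOVA supportive settles the order. The third is that the imbalance-driven covariate rule affects the primary test: it applies only to the adjusted analyses.

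What the objection does not show is any setting in which the t-test does better by more than the one degree of freedom.

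**Conclusion.** The point holds as an efficiency recommendation for the randomised comparison in the sub-study. It is not an error of validity, and it does not touch the main trial. ANCOVA is at least as precise as the change-score t-test, up to one degree of freedom, whatever rho and the SD ratio are.

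From a nominal 80% at 48 per group with equal SDs, the gain is about 2 points (rho 0.9) to 14 points (rho 0.3). It shrinks towards nothing as the true slope on baseline approaches 1, and it is small for markers with ample power or if each arm has 96 women. Oxytocin, a marker labelled primary whose tabled n does reproduce, stands to gain about 9 points at rho 0.5 with equal SDs. The direction is certain; the size is not.

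**What to change.** In section 6.4.3.2:
- Make ANCOVA the primary analysis: the 2-hour value on treatment group, baseline value and membrane status (the randomisation stratum that varies within the Yale site). Fix the analysis scale for each biomarker in advance.
- Keep the t-test on change as the supportive analysis.
- In the adjusted analyses, replace the rule that adds covariates because they differed between groups with a short list chosen beforehand for prognosis.

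The cost is one or two degrees of freedom out of 94 and a short amendment to the text. No new participants, samples or assays are needed. When the section is revised, it would help to state whether the table SDs are SDs of change, what rho is assumed, and how the 192 participants relate to 48 per exposure group, so that power can be quoted for the chosen analysis.

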Among the women enrolled in the translational sub-study at Yale, the following secondary outcomes will be explored:

- Plasma proteomic profiles (measured by mass spectrometry) after 2 hours of treatment comparing patients receiving IV oxytocin and nipple stimulation. Plasma samples from patients who have not undergone cervical ripening will be collected as additional control to account for differences achieved from cervical ripening alone. Plasma samples from patients in early spontaneous labor will be obtained to compare how closely nipple stimulation therapy and IV oxytocin approximate the molecular phenotype of spontaneous labor.
- Changes in plasma proteomic profiles from baseline (prior to treatment), 2 hours, and the time of adequate contractions in each treatment group
- Plasma micro-RNA profiles (measured by bulk RNA sequencing) after 2 hours of treatment among patients receiving IV oxytocin, nipple stimulation, and patients in early spontaneous labor.
- Changes in plasma micro-RNA profiles from baseline (prior to treatment), 2 hours, and the time of adequate contractions in each treatment group
- Urine prostaglandin profiles (measured by mass spectrometry) at 2 hours comparing patients receiving IV oxytocin, nipple stimulation, nipple stimulation who cross-over to IV oxytocin, un-ripened control patients, and patients in spontaneous labor.
- Changes in urine prostaglandin profiles from baseline (prior to treatment), 2 hours, and the time of adequate contractions in each treatment group

Among the women enrolled in the translational sub-study for milk collection, the following secondary outcomes will be explored:

- Changes in milk sodium and conductivity levels from before delivery (in the nipple stimulation therapy group only), and 12, 24, 48 hours after delivery. For mothers hospitalized for a longer period, additional samples at 72 hours will be collected or later up to twice a day.
- Milk macronutrient composition at 48 hours after delivery in each treatment group.
- Milk RNA profile at 48 hours after delivery in each treatment group.

The following secondary neonatal outcomes will be explored:

- Intrapartum fetal death or neonatal death (assessed until birth hospitalization discharge or death)
- Neonatal Apgar score ≤ 3 at 5 minutes of life
- Umbilical cord arterial pH < 7.0 or base excess > 12 mmol/L; or umbilical cord venous pH < 7.0 or base excess > 12 mmol/L if arterial blood sample not available

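### The biospecimen response-profile model is limited to CS or HCS covariance, which forces one common correlation; this matters only if three sampling times are in the response, and the protocol leaves that open

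*Protocol*

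**What the plan says.** All of the model text is in Protocol section 6.4.3.2, in the data analysis plan for the biospecimen sub-study.

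- **Primary comparison.** The between-group comparison of change "will be based on a Student's t-test, with a supportive analysis using Analysis of Covariance (ANCOVA").
- **Place of baseline.** The supportive model is one "where the baseline biomarker level will be a covariate in a mean response profile model (MRP").
- **Stated flexibility.** The model is described as one that "allows for different variances and covariances across time".
- **Permitted structures.** The next sentence allows "either compound symmetry (CS) covariance or heterogenous compound symmetry covariance (HCS) to account for the within-patient correlation".
- **Selection rule.** "the choice between the two covariance matrices will be made using a likelihood ratio test (LRT"), on the ground that the two are nested.
- **Use.** The model supplies means and between-group differences with 95% confidence intervals, contrasts within and between groups over time, multivariate Wald tests and the adjusted analyses. Every biomarker in the sample size table is handled the same way.
- **Sensitivity model.** A linear mixed model in actual time, with a random intercept and possibly a random slope for each woman.

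The sampling times are described differently in two places. Section 5.2.2 lists "Changes in plasma proteomic profiles from baseline (prior to treatment), 2 hours, and the time of adequate contractions in each treatment group". Section 6.3 (Biospecimen Procedures) lists before ripening, after ripening and two hours into treatment, with at most three blood samples. It also expects some samples to be missed.

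**The concern.** CS has one variance and one covariance, so if the test retains CS, the fitted model does not have the flexibility that the preceding sentence gives it. HCS frees the variances, but its covariance for times i and j is rho × SD_i × SD_j with a single rho. The likelihood ratio test compares equal with unequal variances and cannot detect a failure of the common correlation. No structure with free correlations, and no robust standard error, is named for this model.

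Samples close in time may well correlate more strongly than samples far apart. If so, a common correlation misstates the variance of a change between two times, and with it the intervals and tests for that change.

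**Working it through.** The plan states no figure on this point, so there is none to reproduce. The check has three parts.

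**1. Parameter counts for T times in the response**

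CS = 2; HCS = T + 1; unstructured = T(T + 1)/2.

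| T | CS | HCS | Unstructured |
|---|---|---|---|
| 2 | 2 | 3 | 3 |
| 3 | 2 | 4 | 6 |

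At T = 2 there is one correlation, so HCS and unstructured are the same model. Fitting HCS to a two-time covariance recovered it to within about 1e-7. At T = 3, HCS is two parameters short of unstructured.

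**2. Does HCS allow different covariances?**

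Take SDs 1, 1.5 and 2 with rho = .6. The covariances are .6 × 1 × 1.5 = 0.9, .6 × 1 × 2 = 1.2 and .6 × 1.5 × 2 = 1.8. Variances and covariances both differ; only the correlations are tied.

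**3. Size at T = 3**

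Assumptions: large sample, complete data, saturated means. Correlations are given as t1t2/t1t3/t2t3. The documents give no correlations, so all of these are assumed.

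With equal SDs, the CS correlation is the mean of the three. For the change between times i and j, the ratio of model SE to true SE is sqrt((1 − mean rho)/(1 − rho_ij)). Type I error is 2 × (1 − Phi(1.96 × ratio)).

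- **.7/.5/.7**, mean (.7 + .5 + .7)/3 = .633. For t3 − t1: sqrt(.367/.5) = 0.856, error about 9.3%. For t2 − t1 and t3 − t2: sqrt(.367/.3) = 1.11, error about 3%.
- **.8/.4/.6**, mean .6. For t3 − t1: sqrt(.4/.6) = 0.816, error about 11.0%. For t2 − t1: sqrt(.4/.2) = 1.41, error about 0.6%. For t3 − t2: sqrt(.4/.4) = 1, error 5%.

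Fitting both structures by Gaussian likelihood, with equal SDs and with SDs 1/1.5/2, gives these errors for t3 − t1 (100% minus coverage of the nominal 95% interval):

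| SDs | Correlations | CS | HCS |
|---|---|---|---|
| 1/1/1 | .7/.5/.7 | 9.3% | 8.9% |
| 1/1/1 | .8/.4/.6 | 11.0% | 10.3% |
| 1/1.5/2 | .7/.5/.7 | 10.4% | 7.2% |
| 1/1.5/2 | .8/.4/.6 | 10.7% | 7.3% |

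Under HCS in the same four settings, intervals cover 96-99% for t2 − t1, 95-97% for t3 − t2 and 94-96% for the level at t2 or t3. If the true correlation is common (.6), HCS covers 95% throughout.

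**The case against.** The strongest objection is that the text favours two response times. Baseline is named as a covariate, which takes it out of the response. Either list of sampling times then leaves at most two blood values. HCS is then unstructured, and the likelihood ratio test compares CS with the full model. The only remaining loss comes from the test sometimes keeping CS when variances differ; a simulation of that rule gave about 5.3-5.7% error. This stands, but it does not settle the matter. The same paragraph ties the covariance to all the times at which data are collected, and it promises within-group contrasts across time. A within-group change from baseline needs baseline in the response.

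A second objection also stands: the primary comparison is a t-test on change, which needs no modelled correlation, and a random slope in the sensitivity model would relax the common correlation. The point is therefore confined to the supportive and adjusted models. The slope is only a possibility, however, and missed samples would make estimates as well as standard errors depend more on the covariance.

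A third objection is that a parsimonious structure is defensible with 48 women per group, and that covariance detail can be left to an analysis plan. Here, though, the protocol has itself fixed the two options and the test between them, and unstructured costs only two more parameters.

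A reader might infer that neither structure has the stated property. That is not so: HCS does, as the covariances 0.9, 1.2 and 1.8 show.

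**Conclusion.** The point holds as a minor one. The protocol describes a flexible covariance, then permits CS, which is not flexible, or HCS, which is flexible except for one shared correlation that the selection test never examines.

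With two times in the response, almost nothing is lost. With three, the assumed correlations give about 9-11% type I error for the first-to-last change under CS and about 7-10% under HCS, with some other contrasts conservative. These sizes rest on assumed correlations and SDs, large samples and complete data; a truly common correlation removes the HCS error altogether.

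It would be tempting to conclude that the sub-study's confidence intervals are wrong. The documents do not support that: the number of response times is not settled, no correlations are given, the primary t-test is untouched, and nothing here bears on spontaneous vaginal delivery.

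**What to change.** In section 6.4.3.2, state which sampling times form the response vector and whether baseline is a covariate or a response. Replace the CS-versus-HCS likelihood ratio test with an unstructured within-patient covariance, falling back to HCS only if the model does not converge.

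This is safe under both readings: it has 3 parameters at two times, where it equals HCS, and 6 at three, where HCS has 4. The cost is one or two sentences and at most two extra parameters. It also brings the specification into line with the flexibility that the paragraph already claims.

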6.1.2 Method of Assignment/Randomization

Enrolled subjects will be randomly assigned in a 1:1 ratio to both study groups. A web-based randomization sequence will be prepared using blocks of variable sizes, stratified by study site and amniotic membrane status (intact versus ruptured), and maintained centrally by the study statistician. The advantage of this method is that it provides a good probability of balance, and future assignments are unpredictable. A subject's group assignment will be obtained only after the subject is confirmed to continue to meet inclusion criteria, and a study number is entered and locked in using *REDCap* (Research Electronic Data Capture), an established, secure, web-based capture and management tool developed at Vanderbilt University. Although blinding of both subjects and their obstetrical clinicians would be ideal, blinding is clearly not possible in this trial. We will minimize systematic bias by applying the

same standard procedures for other labor and management strategies between groups at each study site. Further, the group assignment of subject will not be taken into account by trained study staff collecting maternal and neonatal outcomes. Importantly, the main study outcomes of spontaneous vaginal delivery and breastfeeding as the sole source of infant nutrition at hospital discharge are objective measures.

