6.4.3 Planned Analyses

6.4.3.1 Primary Analyses

1) Overview: Data analyses will adhere closely to the CONSORT guidelines. Analyses will follow the intention-to-treat principle in which subjects will be analyzed in the group to which they were randomized, regardless of whether or not they received the assigned intervention.

2) Primary Analyses:

Descriptive statistics will characterize the group of individuals recruited and investigate comparability of the two study groups at baseline. Formal statistical testing will be limited to select baseline characteristics considered to be prognostic factors for the primary outcome including hospital admission body mass index (BMI), primary indication for labor induction, Bishop score at randomization, and birth weight. Categorical variables will be compared between trial groups by using the Chi-squared or Fisher's exact tests as appropriate, and continuous variables will be compared using Student's t-test or Wilcoxon Rank Sum Test, as appropriate. Distributions of continuous variables will be assessed by visual inspection of histograms.

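### The adjusted biomarker model takes its additional covariates from observed between-group differences instead of a list fixed in advance

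*Protocol*

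**What the plan says.** Protocol 6.4.3.2, in the data analysis plan for the biospecimen sub-study, sets out three layers for the change in each biomarker from baseline to 2 hours.

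- **Primary test.** "This unadjusted between-group comparison of the within-group change will be based on a Student's t-test".
- **Supportive model.** An analysis of covariance "where the baseline biomarker level will be a covariate in a mean response profile model (MRP", so the baseline value is fixed in advance.
- **Adjusted analyses.** "we will include in the MRP as covariates the between-group differences identified in the between-group comparisons". No candidate factors, threshold or restriction to baseline variables are given.

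The same section covers a comparison that is not randomised: "Secondary comparisons evaluate the change with labor induction versus spontaneous labor".

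Three other statements bear on the rule. Section 6.1.2 says "Enrolled subjects will be randomly assigned in a 1:1 ratio to both study groups", with site and membrane status as strata. Section 6.4.3.2 gives one purpose of covariate adjustment in the main trial as "to use covariates to improve the estimated difference between treatment groups". Section 6.4.3.1 says of baseline comparisons: "Formal statistical testing will be limited to select baseline characteristics considered to be prognostic factors for the primary outcome", and names admission BMI, indication for induction, Bishop score and birth weight. The primary outcome there is spontaneous vaginal delivery, not a biomarker.

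**The concern.** Between arms formed by randomisation, a difference in a baseline factor arises by chance. Its size says nothing about whether the factor predicts the biomarker. A rule that admits factors because they differ can therefore bring in irrelevant ones and leave out strong predictors that happen to balance. Membrane status is the clearest case: stratification pushes it towards balance, so the rule will usually exclude the one factor, besides baseline, that the design itself gives reason to include. (Site, the other stratum, does not vary in the Yale sub-study.)

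The rule also means that the adjusted model is unknown until the data are seen. With no candidate list or threshold, two analysts could reach different models. As worded, it does not exclude differences that arise after randomisation.

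At stake are the precision and predictability of the adjusted estimates, not the validity of the primary biomarker test.

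**Working it through.** The plan gives no figure for this rule, so there is none to reproduce. From Protocol 6.4.2 I take 48 per group, two-sided alpha 0.05 and 80% power. Everything labelled assumed below is not in the protocol.

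**1. How often the rule selects anything.** For k independent baseline factors tested at 0.05 (assumed threshold), the chance of at least one difference is 1 − 0.95^k.

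- k = 4 (the number of factors named in 6.4.3.1): 1 − 0.8145 = 18.5%
- k = 6: 26.5%
- k = 10: 40.1%

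In most trials the rule would add nothing.

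**2. What one pre-specified prognostic covariate would add.** Let the outcome SD be what remains after baseline biomarker adjustment. Take an effect of 0.578 of that SD, chosen to give 80% power. The noncentrality is 0.578 × √(48/2) = 0.578 × 4.899 = 2.832, and with 94 degrees of freedom power is 80.0%. A covariate with residual correlation r divides the SD by 1/√(1 − r²), so the noncentrality becomes 2.832/√(1 − r²), with 93 degrees of freedom.

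| Assumed r | √(1 − r²) | Noncentrality | Power |
|---|---|---|---|
| 0.1 | 0.995 | 2.846 | 80.4% |
| 0.2 | 0.980 | 2.890 | 81.6% |
| 0.3 | 0.954 | 2.968 | 83.6% |
| 0.4 | 0.917 | 3.090 | 86.4% |
| 0.5 | 0.866 | 3.270 | 89.9% |

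The gain runs from almost nothing to about 10 points.

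**3. What the imbalance rule delivers.** Simulation with 48 per group and 4,000 runs per scenario. Assumed: six candidates, three of them prognostic and together explaining R² of the remaining variance; a covariate enters if its t-test between arms gives p < 0.05.

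| Assumed R² | Mean SE, rule | Mean SE, pre-specified | Power, rule | Power, pre-specified | Type I error, rule |
|---|---|---|---|---|---|
| 0.1 | 0.206 | 0.197 | 80% | 82% | 4.9% |
| 0.3 | 0.204 | 0.173 | 80% | 91% | 4.1% |
| 0.5 | 0.202 | 0.146 | 82% | 97% | 3.5% |

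Without covariates the SE is about 0.203 and power 79–80%. No covariate was selected in about 73% of runs, in line with step 1 (100 − 26.5 = 73.5%). A second simulation, with eight candidates of which one was correlated 0.5 with the outcome, gave 80% power without covariates, 79% under the rule and 90% with that covariate pre-specified; type I error under the rule was 4.7%.

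The rule recovers little of the available precision. Its type I error is at or below the nominal 5%, so it errs towards conservatism.

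**The case against.** The strongest defence is that little depends on this sentence. The primary biomarker comparison is unadjusted, and the sub-study was sized on that comparison. The natural covariate, the baseline biomarker level, is already fixed in the same model. All of this stands and sets the weight of the point.

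It also rules out some stronger readings. A reader might infer that the adjusted analysis gains almost nothing over the t-test. The documents do not support that, because whatever precision the baseline level brings is kept; only what other factors add beyond it is in question. A reader might also infer that selecting covariates from the data produces false positives, but the simulations show no inflation. Finally, the 90% power figure might be taken as an estimate for this trial. It is the top of an assumed range, since the protocol gives no correlation between any clinical factor and a biomarker change.

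A second defence is that observed differences need not be chance. For induction versus spontaneous labor this is right: those controls are recruited separately, and differences may be real confounding. Section 6.3 also allows samples to be missed, for example when delivery comes before the time point, so the analysed subset may differ between arms for reasons arising after randomisation. The criticism is therefore confined to the randomised contrast. Neither situation favours the rule, though: at about 48 per group, selection by significance can miss real confounders.

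Third, nothing in the protocol shows that BMI, Bishop score or gestational age predict these biomarkers. That stands too, and the choice of such factors belongs to the investigators.

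**Conclusion.** The point holds as a minor one. For the randomised comparison, the protocol commits its adjusted, supportive biomarker model to additional covariates chosen by observed difference. The rule takes no account of prognostic value, works against including membrane status, and leaves the model open until the data are seen. Because the rule is written into the protocol, it is not merely a detail left for the statistical analysis plan.

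The cost is forgone precision in a supportive analysis: about 0 to 10 points of power for one covariate with residual correlation between 0.1 and 0.5, and more only if several factors together explain a large share of the remaining variance. These sizes rest on assumed correlations, candidate counts and a 0.05 selection threshold. The primary t-test and the baseline-biomarker adjustment are unaffected.

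**What to change.** Replace the sentence in Protocol 6.4.3.2 with a covariate list fixed before comparative biomarker data are examined and used whatever imbalance is observed. The list should:

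- keep the baseline biomarker level;
- add membrane status, because it is a randomisation stratum;
- include a few baseline factors already collected that the investigators judge prognostic for the biomarkers, with gestational age, BMI and Bishop score as possible examples.

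For the spontaneous-labor comparison, name the confounders in advance and do not select them by significance.

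The cost is a short text amendment. It needs no new data or participants and does not change the primary test.
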